Aim 1 (Strategy 1): Modulating the limbic system as an approach to treatment: mPFC iTBS. Cigarette smokers will be randomized to receive 10 days of real iTBS or sham iTBS directed to the mPFC. Intermittently the desire to smoke, cigarette value using behavioral economic demand, preference for immediate gratification (delay discounting), and cigarette self-administration will be assessed. Smoking cue-evoked brain activity will also be measured when individuals are asked to 'crave' (passive limbic engagement) versus 'resist' the craving (executive engagement)(7,11-13). We hypothesize that iTBS will: 1) decrease the behavioral smoking measures described above, which will be explained by a selective 2) decrease in the neural response to cues when individuals 'allow' themselves to crave, and 3) sustain these changes over a time period sufficient to overcome the initial quit attempt (~7-14 days).

Aim 2 (Strategy 2): Modulating the executive system as an approach to treatment: dlPFC iTBS. Aim 2 will follow the design of Aim 1. The procedures will be identical, except iTBS will be delivered to the left dlPFC. We hypothesize that iTBS will: 1) decrease the behavioral smoking measures described above, which will be explained by a selective 2) increase in the neural response to cues when individuals attempt to 'resist' the cues, and again 3) sustain these changes over a similar period as specified in Aim 1.

Exploratory Aim- Evaluate baseline frontal striatal connectivity and discounting rate as factors to predict an individual's likelihood of responding to Strategy 1 versus Strategy 2. We will test the hypotheses that individuals with a higher ratio of (mPFC-striatal)/(dIPFC-striatal) connectivity will be more likely to have a behavioral change after Strategy 1. Various demographics (e.g. gender, smoking history, socioeconomic status, subclinical depressive symptoms, self-efficacy, & motivation to quit will be evaluated as explanatory variables.

The outcomes of the present aims will resolve a critical gap in our knowledge regarding the relative efficacy of 2 promising TMS treatment strategies. These outcomes will be directly translated to a larger longitudinal study evaluating a multipronged approach to improving outcomes in traditional pharmacotherapy or behavioral treatments.

Methods and Measures

Design

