Study Visit Procedures: At all visits, individuals will provide a urine screen to detect recent use of drugs of abuse and pregnancy, a breath carbon monoxide (CO) sample to detect recent cigarette smoking, and a breath sample to test for recent alcohol use. During the consent visit, visits 1, 6, 10 and follow up visits samples will be collected to determine cotinine (nicotine metabolites) levels in the urine. Samples will be taken from the urine sample provided for the drugs of abuse screen, no additional samples will be required from the participant. At visits 1, 6, 10 and follow up visits (Assessment visits), participants will complete a battery of behavioral assessments following active TMS or sham (see Table 2). MRI scanning (at visits 1 and 10) will occur prior to TMS in order to isolate cumulative, rather than acute, effects of TMS. At all visits participants will be required to provide a CO reading at least 50% of their baseline CO measure to ensure they are at least 6 hours deprived from cigarettes. Cigarette deprivation will be use to increase craving and responding for cigarettes. Short term cigarette deprivation has known amplification effects on the brain response to smoking cues (93, 94). Moreover, we have extensive experience with successfully using this deprivation procedure (33, 41).

Table 2 1. Biochemical and self-report assessment of tobacco use and dependence						
Measure	Time (Min.)	Visits	Description			
Carbon monoxide (CO Level)	1	1-10, and follow-ups	Breath CO provides an accurate measure of recent exposure to CO , including from smoking combustible tobacco products (95). The CO measurement will be used to determine recency of smoking.			
Timeline Follow-Back (TLFB) interview	5	1, 6, 10, and follow-ups	This self-reported tobacco product use interview asks participants to retrospectively estimate the number of tobacco products they've used each day for the past 30 days or since the previous assessment, whichever is fewer (89).			
Fagerström (FTND)	3	1, 6, 10, and follow-ups	This 6-item questionnaire quickly assesses degree of cigarette dependence (96, 97). Test for Cigarette Dependence.			
2. Measures of t	tobacco pr	oduct value an	d sensitivity (**PRIMARY DEPENDENT MEASURES)			

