Functional MRI Smoking Cue Reactivity Task (acquired after behavioral assessments)	15	1, 10	This task has been used in 4 original research publications by our group and reliably activates orbitofrontal and medial prefrontal regions (7, 11- 13). We will give participants an unlit cigarette to hold in their hand while they are in the MRI scanner. They will receive two 12m runs of the task (fixed within subject, counterbalanced within groups). During one run they will be instructed to 'allow' themselves to crave (passive limbic engagement) and in the other run they will be told to 'resist' the cues (executive engagement). When the task begins participants are shown pseudorandomly interspersed blocks of images: 1) cigarette images (e.g., cigarettes, lighters, people smoking) (CIG), 2) neutral images,			

			chromatically matched to the CIG images (NEU), and 3) blurry non- images (BLUR). Stimuli are presented in six 120-s epochs, each consisting of four 24-s blocks of an image type (one block each of CIG, NEU, BLUR). Each block is followed by a 6-s washout period, allowing the hemodynamic response from the previous block to decline before the next is presented. Scanning parameters: Multislice gradient-echo echo planar imaging (TR=2200, TE=35 msec, field of view of 192 mm, voxel size 3.0 x 3.0 x 3.0 mm, 36 slices, 3 mm thickness, no skip).
2. Other Assessm	ents		
Confidence in Active or Sham TMS Assignment (Active vs Sham)	1	1, 6, 10	Participants will complete a form indicating their confidence (scale 1-10) in whether they are receiving active or sham treatment. Pooled accuracy from prior work in our collaborator's laboratory was 47.6% suggesting that individuals were not aware of the stimulation being received.
Minnesota Nicotine Withdrawal Scale (MNWS)	2	1 - 10 and follow-ups	Participants will be asked to rate a variety of mood and physiological symptoms associated with nicotine withdrawal (e.g., anxiety, attention, hunger). Total withdrawal scores will be measured using the 8-item MNWS originally adapted from Hughes and Hatsukami 1986 (102) and Hughes 1992 (103). The 8-item scale is a validated measure and the most frequently used (104, 105).
Beck Depression Inventory (BDI)	10	1,6,10,and follow-ups	Given that iTBS to the left dlPFC improves depression scores, we will perform a mediation analysis to determine if any effects observed on smoking behavior and the brain response to smoking cues is related to changes in depression

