Behavioral Outcomes: For the treatment phase (10 days of real/sham TBS), the primary behavioral outcomes include Cigarette demand (Q0 and alpha), Craving (QSU Intention, QSU Relief), and Delay Discounting (\$100 and \$1000). For the treatment phase the analysis will be performed using repeated measures ANOVA on change scores from baseline for each visit. The main independent variable in the ANOVA will be time (visits on day 1, 6, 10), group (real or sham) and their interaction. For correlations of observations across visits an AR(1) structure will be considered and compared with other structures such as compound symmetry and a general structure. The primary hypothesis is the interaction. If the interaction effect for an outcome is significant, we will conclude there is statistical evidence of overall treatment effect. If the spaghetti plots suggest trends (e.g., linear, quadratic, or piecewise changes) we will treat time as a continuous variable and fit repeated measures regression models along with group and its interaction with continuous time as independent variables.

Neuroimaging Outcomes: For the treatment phase, primary analysis. Image pre-processing will be conducted with FSL v. 5.0: (FMRIB Analysis Group, Oxford, UK) (108) realignment to the first volume, smoothing with an anisotropic 8-mm Gaussian kernel, high-pass filtering, resampling to 2-mm isotropic voxels, and stereotactic registration to the Montreal Neurological Institute 152-subject average template. Subjects with >3 mm movement (total mean frame displacement across the entire task) will be excluded from analysis.

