Hypothesis Aim 1: Based on the framework predicted by CNDS theory, and preliminary work (see Study 4), we anticipate that mPFC stimulation will lead to a decrease in brain reactivity to cues during the "allow" condition (passive limbic engagement). We will analyze the neuroimaging data in concert with the behavioral data, evaluating the hypotheses that 1) mPFC iTBS will decrease the brain reactivity to cues in the 'allow' condition (with no consistent link to the 'resist' condition) and that 2) this will be related to the behavioral change in a dose-dependent manner. This will be achieved by extracting the average BOLD signal timecourse and the percent signal change during the CIG versus NEU blocks from a priori anatomically defined regions of interest (ROIs), including the striatum (ventral striatum and dorsal striatum), insula, inferior frontal gyrus, and anterior cingulate cortex. Ventral striatal and dorsal striatal ROIs are derived from the FSL Oxford-GSK-Imanova striatal atlas, mapped via probabilistic diffusion tractography (109) in agreement with anatomical projection zones from the frontal cortex (1). Hypothesis Aim 2: Based on the framework predicted by CNDS theory, and prior studies of dlPFC stimulation in smokers (4-9), we anticipate that dIPFC stimulation will lead to an increase in executive control circuitry (left dlPFC, posterior parietal cortex) during the "resist" condition (executive engagement). As in Aim 1, we will analyze the neuroimaging data in concert with the behavioral data, evaluating the hypotheses that 1) dIPFC iTBS will decrease the brain reactivity to cues in the "resist" condition (with no consistent link to the "allow" condition) and that 2) this will be related to the behavioral change in a dose-dependent manner. The ROI based outcomes of Aim 2 will be compared with the outcomes of Aim 1 using standard general linear modeling as well as a data-driven hierarchical model (see Integration below). As an experimental control, for both Aims we will also calculate the percent signal change from the primary motor cortex, a region which should not be differentially modulated by mPFC or dIPFC stimulation. Although some studies have used the visual cortex as a control region a recent meta-analysis by our group demonstrated that the visual cortex is typically activated more to drug cues than neutral cues (78). Secondary functional connectivity analysis: Additionally, an exploratory seed-based functional connectivity analysis using psychophysiological interactions (PPIs) will be performed using the TMS stimulated ROIs (mPFC and dlPFC) and the striatal target regions (ventral striatum, dorsal striatum- defined above) as seed regions. These data will be compiled across participants and compared between the mPFC and dIPFC stimulation days. Group analyses will be performed using a random effects model limiting significant clusters to those that meet p<0.05 family-wise error corrected.

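### Both Aims claim that the neural change explains the behaviour change, but the plan tests only whether the two are related, with no arm term, common-cause adjustment or time order stated

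*Combined protocol and SAP*

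**What the plan says.** - **Objectives, Aim 1 and Aim 2.** Each Aim hypothesises that iTBS will "decrease the behavioral smoking measures described above, which will be explained by a selective" change in the neural response to cues (Aim 1 in the craving condition, Aim 2 in the resisting condition).
- **Outcome Measure(s), Neuroimaging Outcomes.** "We will analyze the neuroimaging data in concert with the behavioral data". Two hypotheses follow for each Aim: (1) iTBS changes cue reactivity in the named condition, and (2) "this will be related to the behavioral change in a dose-dependent manner". No model is given for (2).
- **Outcome Measure(s), Behavioral Outcomes.** The treatment-phase analysis is a "repeated measures ANOVA on change scores from baseline for each visit", with time, group and their interaction. It has no neural term.
- **Table 2, Beck Depression Inventory.** "we will perform a mediation analysis to determine if any effects observed on smoking behavior" and on the brain response are related to change in depression. Depression is the mediator there, and the brain response is an outcome.
- **Follow-up phase and Exploratory Aim.** The follow-up analysis uses baseline cue reactivity. The hierarchical model compares the two strategies. Neither takes neural change as the path to behaviour change.
- **Timing.** Study Visit Procedures state that "MRI scanning (at visits 1 and 10) will occur prior to TMS" and that at assessment visits "participants will complete a battery of behavioral assessments following active TMS or sham". Table 2 lists the cue task as "acquired after behavioral assessments". These two accounts of the order within a visit conflict.

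**The concern.** To say that a neural change explains a behaviour change is to say that treatment acts on behaviour through the brain measure. A relation between two change scores does not establish that. Two rival accounts give the same relation with no path from brain to behaviour:

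- TMS moves both measures by separate routes. The arms then differ on both, and pooling the arms creates a correlation.
- Something else moves both. Study Visit Procedures name a candidate: cigarette deprivation raises craving and also amplifies the brain response to cues.

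Scans take place only at Visits 1 and 10, so there is one neural change. It ends at the visit where treatment-phase behaviour also ends. A relation between the two therefore has no built-in time order.

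At stake is the mechanistic conclusion. The Objectives intend the outcomes to feed a larger study, and a circuit could be carried forward as the explanation on the strength of an association.

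**Working it through.** **The plan's own figure.** Sample Size gives 28 per group for d=0.8, 80% power and 5% type 1 error. The simple two-sided calculation is n = 2(1.96+0.84)²/0.8² = 24.5, so 25 per group (26 with the t distribution). Allowing 10% loss, 25/0.9 = 27.8, so 28. The figure is reproduced, though the AR(1) correlations are not given and the repeated-measures version cannot be rerun. It sizes a group comparison. The plan gives no figure for the brain–behaviour relation.

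**Inputs from the documents.** There are 69 per Aim, 46 active and 23 sham. At 78% retention, 46×0.78 = 35.9 and 23×0.78 = 17.9, so 36:18. After 10% imaging loss, 35.9×0.9 = 32.3 and 17.9×0.9 = 16.1, so 32:16. COVID-related missed scans come on top and are not quantified. The effect is d=0.8, applied here to both measures.

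**Assumptions.** The test is two-sided at 5%, counting only relations in the predicted direction, so the nominal rate is 2.5%. The shared-cause correlation ρ is not in the documents; 0, 0.3 and 0.5 are used.

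**Separate routes only.** With 2:1 allocation, the correlation created by pooling is (2/9)d² / [1+(2/9)d²]. At d=0.8 this is 0.142/1.142 = 0.125.

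**Simulation (4,000 runs per setting).** Brain change is M = 0.8T + √ρ·U + √(1−ρ)·e₁. Behaviour change is Y = 0.8T + √ρ·U + √(1−ρ)·e₂. T is arm and U the shared cause, and there is no effect of M on Y. False-positive rates at 36:18:

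| ρ | Pooled relation | Pooled relation, arm effect on M also required | Arm-adjusted relation, arm effect on M also required |
|---|---|---|---|
| 0 | 14.4% | about 12% | 1.8% |
| 0.3 | 84.7% | about 69% | 46.5% |
| 0.5 | 99.7% | about 78% | 75.9% |

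At 32:16 the pooled rates are about 13%, 80% and 99%, and the last column becomes 1.8%, 38.9% and 69.0%. In the active arm alone at 36:18 the relation is positive in 2.6%, 43.8% and 90.4%. Avoiding pooling therefore removes the separate-routes problem but not the shared-cause one.

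The 78% is close to a ceiling. Power for the arm effect on M at d=0.8 and 36:18 is 77.6%, so with ρ=0.5 the mechanism claim follows almost every time the brain effect is detected.

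**Power when the path is real.** With an arm effect of 0.8 SD on M and Y = bM + e, the arm-adjusted joint test has power 42% (b=0.3) and 71% (b=0.5) at 36:18, and 37% and 65% at 32:16.

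**A time-ordered alternative.** One could regress 1-week follow-up behaviour on Visit 10 neural response, adjusted for Visit 10 behaviour. If mediation is already fully expressed by Visit 10 (assumed stability of behaviour 0.7), power is about 2%, because the adjustment removes the effect being sought.

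**The case against.** The strongest reply is that the plan does more than correlate two changes. Hypothesis (1) already tests the iTBS effect on the brain, and the behavioural ANOVA tests the arm effect on behaviour. The hypotheses also demand specificity: an effect in one instruction condition without a consistent link to the other, with primary motor cortex as a control region. A global improvement would be expected to show in both conditions.

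Much of this stands. A reader might infer that the plan would declare a mechanism in 60% or 98% of trials when TMS does nothing to the brain, since the relation alone is positive that often at ρ=0.3 or 0.5. The documents do not support that as the plan's false-claim rate: once hypothesis (1) must also hold, the rate falls to about 2–3%. The specificity checks are useful too, but they do not test a path, and a shared cause that acts mainly in the craving condition would pass them.

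The documents also do not say that arms are pooled, nor which visit's behaviour enters the relation. The 12–14% figures apply only if arms are pooled without adjustment.

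**Conclusion.** The mismatch holds. The Objectives state an explanation, the analysis tests a relation, and no other part of the plan tests neural change as the path.

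Under pooling and separate routes at d=0.8, the false-positive rate is about 13–14%, or about 12% with the arm effect on the brain required, against 2.5%. This uses the protocol's own effect size on both measures and needs no assumed correlation. The much larger rates rest on an assumed shared-cause correlation of 0.3 or 0.5, for which the documents give no value.

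A reader might also infer that adding arm to the model keeps false claims at 5% or below. It does so without a shared cause (about 2%). With one, the arm-adjusted joint test still fails in about 47% or 76% of trials at 36:18. No same-visit test here separates mediation from a shared cause, so the conclusion has to be limited as well as the model improved.

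This concerns the mechanistic claim only. It should be corrected, but it does not touch the real-versus-sham comparisons.

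**What to change.** 1. **Neuroimaging Outcomes, hypothesis (2), both Aims.** Specify the brain–behaviour model and name the behavioural visit. Include arm, baseline ROI response, baseline behaviour, and the CO and cotinine already collected. Require the arm effect on the ROI as well. After the quit date, CO and cotinine also register smoking itself, so report the model with and without them.
2. **Objectives.** Replace the claim of explanation with one of association. Report the result as consistent with mediation only if both steps hold and a sensitivity analysis for unmeasured common causes is shown.
3. **Follow-up model.** The 1-week model adjusted for Visit 10 behaviour can be a supporting time-ordered analysis. It should not be the main test, for the reason given in the working.
4. **Reconcile two points that the model depends on.** One is the order of scan and behavioural battery within a visit. The other is the predicted direction for Aim 2: the Objectives expect an increased neural response while resisting, but hypothesis (1) expects decreased reactivity.

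The cost is SAP wording and one specified model per Aim, with no new data. Power for the mechanism claim is modest, about 37–42% for a path of 0.3 and 65–71% for 0.5, before any loss from the added covariates or missed scans. The plan should say so.

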The long term goal of the research is to develop non-invasive brain stimulation as an evidence-based tool to facilitate abstinence during the first week after a quit attempt, as this is a robust predictor of 6-month treatment outcomes with traditional pharmacotherapeutic and behavioral interventions. The next step in pursuit of that goal is to systematically and parametrically evaluate the efficacy of two promising TMS treatment strategies (LTP-like stimulation to the mPFC (Aim 1), LTP-like stimulation to the dIPFC (Aim 2)) as tools to change smoking behavior and brain reactivity to smoking cues. These aims will be addressed in serial (Aim 1 Years 1-3, Aim 2 Years 3-5). A randomized, double-blind, sham-controlled design will be used for each aim. In total, 138 smokers will be recruited from the tri-county area surrounding Winston-Salem, NC. Current cigarette smokers seeking to quit smoking and willing to set a quit date will be recruited from the tri-county area using digital and print advertising in diverse media outlets. Following informed consent and screening, participants will be randomized to receive real or sham TMS to the mPFC (Aim 1, Years 1-3) or the dlPFC (Aim 2, Years 3-5) (see Table 1 and TMS Procedures below for more details regarding sham controls and double blinding procedure). During the Treatment Phase, participants will receive 10 sequential days of TMS (with additional behavioral and MRI scanning (see Table 1). Participants will receive TMS at least 3 times a week for a total of 10 TMS sessions. During the follow-up phase, participants will receive 4 maintenance TMS sessions once a week for 4 weeks. During the Follow Up Phase, behavioral assessments will be acquired weekly for the first 4 weeks (see Table 2), and daily EMA will be acquired. Consistent with the CNDS model, the primary hypotheses are that LTP-like stimulation to the mPFC and LTP-like stimulation to the dlPFC will both lead to a decrease in

smoking cue-reactivity in the salience network (neuroimaging outcome), and cigarette value (behavioral outcome) but that directly targeting the value circuit (mPFC) will be more efficacious. Additionally, we will test the hypothesis that individuals with higher discounting rates and cigarette valuation at baseline will respond more to the stimulation strategies compared to those with lower baseline discounting and valuation (Exploratory Aim).

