Table 1. Study Design. Aim1&2 will be conducted sequentially. *Quit date, ^primary						Treatment Phase^				Follow up Phase#					
goal: evaluate 2 TMS strategies as tools to enhance cessation in the critical first week					1*	2-5	6	7-9	10	1 wk	2 wk	3 wk	4 wk	8-24 wks	
after a quit date. #secondary goal: durability			Behavior (Lab)	Х		Х		Х	Х	Х	Х	Х			
ള	Grou	Group Assignment			Neuroimaging	Х				Х					
 	Aim 1	vmPFC	Real	κ Ι									\vdash		
eel		vmPFC	Sham	$\mathbf{\lambda}$	TMS	X	Х	Х	Х	Х					
SC.	Aim 2	un?FC	Real	$\langle \rangle$	EMA (daily,	Х	х	Х	х	Х	X	Х	х	Х	Х
0,		un?FC	Sham		remote)										

Setting

All study activities will take place at Wake Forest University of Health Sciences (WFUHS).

[name] primary office and research laboratory is located in the Clinical Neuromodulation Laboratory in the Department of Cancer Biology. [name] lab space will include a room dedicated for all research related activities including a space for screening participants and a space dedicated for TMS stimulation. It will contain a computer and desk for participant interviewing and a TMS system.

The MRI portion of the study will take place at the MRI center located on [name]. This will utilize the Siemens 3T scanner in the MRI center.

Finally, recruitment efforts will come from the local community using flyers as well as traditional and social media outlets (radio, television, Facebook, Craigslist, local newspapers). Collaborative efforts will be maximized in order to recruit subjects from the associated Wake Forest University smoking programs.

Subjects selection criteria

We anticipate that we will be able to recruit 138 eligible individuals from the communities surrounding WFUHS. We anticipate that 56% of subjects will be male and 44% female, and that approximately 14% of subjects will be racial and ethnic minorities. The risks of MRI and TMS to the unborn fetus are not well understood. Therefore, to be included, females must not be pregnant as determined by a urine pregnancy test and must be utilizing reliable birth control during the course of the study.

Inclusion Criteria

1. Age 18-75 (to maximize participation, and minimize effects of cortical atrophy on neuroimaging data)

- 2. Current cigarette smoker (at least 10 cigarettes per day)
- 3. Able to read and understand questionnaires and informed consent.
- 4. Has accommodations within 50 miles of the study site.

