Study Visit 1 (Behavior, MRI, TMS) will begin 1 week prior to the quit date. **Inclusion/Exclusion criteria:** To participate in the present study, participants must: 1) be 18-75 years of age, (2) smoke at least 10 cigarettes a day (on average; as measured by 1 month timeline follow-back (TLFB), (3) not have a history of or current psychiatric or neurologic disease, or traumatic brain injury (4) not be pregnant, , (5) not currently use psychoactive substances other than alcohol, nicotine, or marijuana; nor have current or recent (e.g. within the past 5 years) moderate/severe substance use disorder (DSM-V) (6) not have any barriers to making contact between the TMS coil and the skin (e.g. braids that cannot be removed), and 7) meet all criteria on a standardized MRI/TMS safety screen (TASS) (including but not limited to implanted electronic devices, bullets or metallic fragments, hair clips and piercings that cannot be removed). These inclusion/exclusion criteria are those used in Study 4 described in Preliminary Research. **Randomization.** Participants will be individually randomized and assigned to treatment or control conditions using stratified block randomization (with blocks of randomly varying sizes) prior to the study.

Experimental Procedure (Aim 1 and 2): Screening Visit – Consent. Participants will receive a series of assessments designed to evaluate nicotine dependence and use, psychiatric conditions, and mood. These include a standard clinical intake evaluation screen for research (used in other studies by the PI), MINI International Neuropsychiatric Interview (MINI 5 P) (88), Timeline Follow-Back (TLFB) (89), Beck Depression Inventory II (BDI) (90), State-Trait Anxiety Inventory (STAI) (91) and Profile of Mood States (POMS) (92). Data will be collected using REDCapTM, and entered directly into the online portal to ensure security and prevent data loss.

During COVID-19, study personnel will interact with participants via the Wake Forest Baptist Health (WFBH) institutional WebEx videoconference software as necessary. Participants will remotely sign and date the informed consent document.

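### Four weekly maintenance TMS sessions in follow-up are missing from Table 1 (14 sessions against 10); if given, weeks 1-4 show effect under maintenance, not durability of the 10-session course

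*Combined protocol and SAP*

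**What the plan says.** The Design section of Methods and Measures describes the treatment phase as follows: "Participants will receive TMS at least 3 times a week for a total of 10 TMS sessions". It then adds that during follow-up "participants will receive 4 maintenance TMS sessions once a week for 4 weeks". In the same phase "behavioral assessments will be acquired weekly for the first 4 weeks", and EMA is collected daily.

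Table 1 has a TMS row with five marks, which match its five treatment columns, and a follow-up phase labelled "secondary goal: durability". Aim 1, the heading of the TMS Treatment section and the Behavioral Outcomes paragraph all describe ten days of stimulation. The maintenance sessions appear nowhere else: not in the TMS procedures, not in the sham and blinding text, and not in the follow-up-phase analysis paragraph.

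On order within a visit, Study Visit Procedures says that at visits 1, 6, 10 and the follow-up visits "participants will complete a battery of behavioral assessments following active TMS or sham".

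**The concern.** Two parts of the plan prescribe different doses. Staff working from the Design text would give 14 sessions; staff working from Table 1 would give 10.

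The difference also changes the meaning of the follow-up data. The Background names the durability of TMS effects on smoking as an open question, and the Objectives present theta burst as an acute intervention from which people move on to other support. A reader would therefore take the follow-up phase to ask whether the effect of the course lasts. With stimulation continuing every week, the laboratory measures in those weeks answer another question: how real and sham differ while treatment goes on. The follow-up-phase analysis allows contrasts of the groups at individual time points, so weekly comparisons are foreseeable, yet nothing says whether they are on or off stimulation.

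**Working it through.** **Session count.** The treatment columns of Table 1 are 1, 2-5, 6, 7-9 and 10, so 1 + 4 + 1 + 3 + 1 = 10 sessions, which reproduces the plan's figure. Adding the maintenance sessions gives 10 + 4 = 14, and 4/10 = 40% more.

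**Reading of Table 1.** The table layout is damaged in the text available here, so the empty follow-up cells are inferred from the marks. The counts fit: the laboratory row has 7 (visits 1, 6, 10 and weeks 1 to 4), the EMA row has 10 (every column), and the TMS row has 5 (the treatment columns only).

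**Maintenance sessions before each laboratory battery.** Assume that follow-up weeks count from session 10 and that one maintenance session falls in each of weeks 1 to 4. At week k the number already given is k - 1 if the battery comes first and k if TMS comes first.

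| Follow-up week | 1 | 2 | 3 | 4 |
|---|---|---|---|---|
| Battery first | 0 | 1 | 2 | 3 |
| TMS first | 1 | 2 | 3 | 4 |

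Weeks 2 to 4 (3 of 4 batteries) follow at least one maintenance session either way. Under the order that Study Visit Procedures gives for follow-up visits, and if session and battery share a visit, week 1 does too, so none of the 4 is free of maintenance. Table 1 shows no laboratory assessment after week 4.

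**Days since last stimulation.** Without maintenance: 7 at week 1 and 14 at week 2. With maintenance: at week 2, at most about 7, and 0 if TMS is given first on the same day; at week 1, 7 with the battery first, or 0 with TMS first on the same day.

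**Effect on the 7-14 day hypothesis.** Aim 1 expects stimulation to "sustain these changes over a time period sufficient to overcome the initial quit attempt (~7-14 days". Its position relative to session 10 depends on the starting point. Visit 1 to session 10 takes 9 days (consecutive days), 11 (weekdays) or 21 (three per week).

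- Quit date at visit 1 (Table 1): 7 - 9 = -2 to 14 - 9 = +5; -4 to +3; -14 to -7. No follow-up battery falls inside.
- Quit date 7 days after visit 1 (Participants and Procedure): +5 to +12; +3 to +10; -7 to 0. The week-1 battery (+7) falls inside for the first two schedules.
- Counted from session 10: +7 to +14. The week-1 and week-2 batteries fall inside.

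**The case against.** The strongest reply is that the plan never defines durability as persistence after stimulation stops. A 10-session course followed by weekly maintenance is a legitimate strategy, and no stated analysis fails because of it. The named follow-up test relates baseline cue reactivity to behavioural change and is not a persistence test. All of this stands. It limits the point to an undefined dose and an undefined target of estimation; it does not remove the mismatch between the Design text and Table 1.

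A reader might infer several stronger things that the documents do not support.

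- *The 7-14 day hypothesis becomes untestable.* Its wording refers to the quit attempt, so the quit date is the more natural starting point. The window then reaches the week-1 battery at most, and in some schedules it lies wholly within treatment. Week 2 is involved only if one counts from session 10, which the plan does not say.
- *The order of battery and TMS at follow-up cannot be read from the text.* The contrary evidence concerns MRI visits only: "Study Visit 1 (Behavior, MRI, TMS) will begin 1 week prior to the quit date" describes visit 1, and the note that the fMRI task is "acquired after behavioral assessments" applies to visits 1 and 10. The only order rule that covers follow-up visits puts the battery after TMS.
- *The week 1-4 comparison is biased.* If maintenance follows the assigned arm, it is still a randomised comparison of real with sham. The plan does not state this for maintenance, although its blinding procedure uses a participant-specific code at each TMS visit, which points that way.

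**Conclusion.** The point holds, as a matter of dose and interpretation. The plan prescribes 10 or 14 sessions depending on the section. If the four extra sessions are given, the laboratory data at weeks 2 to 4 in any order, and at week 1 under the plan's own order when session and battery share a visit, describe the effect under weekly maintenance TMS. They cannot show that the effect of the 10-session course persists.

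This rests on three assumptions: follow-up weeks run from session 10, maintenance falls in weeks 1 to 4, and the blank TMS cells in Table 1 are as the mark count implies. Whether session and battery share a visit is not stated and matters only for week 1.

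The primary comparison over visits 1, 6 and 10 is not touched, because maintenance comes after it. What is affected is the secondary durability conclusion. No numerical effect on any estimate can be derived from the documents.

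**What to change.** 1. Make Table 1 and the Design section agree on 10 or 14 sessions. If 14, mark the maintenance sessions in Table 1, state their weeks, say whether they share a visit with the battery, and state that they are given by assigned arm.
2. If maintenance is kept, report weeks 1 to 4 as *effect under weekly maintenance TMS*. Base any off-stimulation statement only on the daily EMA already collected: between session 10 and the first maintenance session (persistence after 10 sessions), and after the last one (persistence after a 14-session course). The plan does not describe the EMA content, so name the item to be used.
3. Keep one order of battery and TMS across all assessment visits. Moving the battery ahead of TMS at follow-up visits alone would change the measurement condition between visit 10 and week 1. An acute effect present at visit 10 and absent at week 1 could then pass for decay.

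The cost is a narrower secondary durability claim, with no added visits. If maintenance is deleted instead, weeks 1 to 4 can address persistence after the 10-session course, but participants lose four sessions of possible benefit.
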